15.3 Deaths, Other Serious Adverse Events, and Other Significant Adverse Events

15.3.1 Deaths

Population: ALL analysis set

All deaths, deaths within 60 days after first dose, and deaths within 30 days after last dose of trial treatment, as well as reasons for deaths, will be tabulated based on information from all relevant information available in the eCRF:

- Number of deaths
- Number of deaths within 60 days after first dose of trial treatment

CONFIDENTIAL
INFORMATION

35/60

- Number of deaths within 30 days after last dose of trial treatment
- Primary reason of death

In addition, date and cause of death will be provided in individual subject data listings together with selected dosing information (date of first / last administration, dose and number of doses).

Subject listing of deaths includes columns for:

- AEs with fatal outcome (list PTs of AEs with outcome=fatal),
- flag for death within 60 days of first dose of M3814
- flag for death within 60 days of first dose of RT
- flag for death within 60 days of first dose of Cisplatin
- flag for death within 30 days of last dose of M3814
- flag for death within 30 days of last dose of RT
- flag for death within 30 days of last dose of Cisplatin

15.3.2 Serious Adverse Events

Population: SAF analysis set

SAEs will be summarized for each dose level and overall, by SOC, and PT in alphabetical order (please refer to Section 15.2.1 for items to be listed).

In addition, subject listings of SAEs will be provided.

15.3.3 Other Significant Adverse Event

Not applicable.

15.4 Clinical Laboratory Evaluation

Population: SAF analysis set

Local laboratory values converted in standard units (including corresponding normal ranges) will be used for the summaries. Values below the detection limit will be imputed by half of the detection limit.

Laboratory results will be classified according to the NCI-CTCAE version 4.03. Additional laboratory results that are not part of NCI-CTCAE will be presented according to the categories:

below normal limits, within normal limits and above normal limits (according to the laboratory normal ranges).

Common Terminology Criteria (CTC) gradable parameters

In this trial, Common Terminology Criteria (CTC) gradable parameters are the following:

Category	Parameter (LBTEST)	Parameter code (LBTESTCD)	Name in NCI-CTC	Direction of abnormality
Biochemistry				
Electrolytes	Calcium	CA	Hypocalcemia/Hypercalcemia	Low/High
Electrolytes	Magnesium	MG	Hypomagnesemia/Hpermagnesemia	Low/High
Electrolytes	Phosphorus (Phosphate)	PHOS	Hypophosphatemia	Low
Electrolytes	Potassium	K	Hypokalemia/Hyperkalemia	Low/High
Electrolytes	Sodium	SODIUM	Hyponatremia/Hypernatremia	Low/High
Enzymes/cardial	Creatinine Phosphokinase	CK	CPK increased	High
Enzymes/liver	Alanine Aminotransferase	ALT	Alanine Aminotransferase increased	High
Enzymes/liver	Alkaline Phosphatase	ALP	Alkaline Phosphatase increased	High
Enzymes/liver	Aspartate Aminotransferase	AST	Aspartate Aminotransferase increased	High
Enzymes/liver	Gamma-glutamyltransferase	GGT	GGT increased	High
Enzymes/liver	Total bilirubin	BILI	Blood bilirubin increased	High
Metabolism	Glucose	GLUC	Hypoglycemia/Hyperglycemia	Low/High
Metabolism	Uric acid ⁽¹⁾	URATE	Hyperuricemia	High
Plasma proteins	Albumin	ALB	Hypoalbuminemia	Low
Renal/kidney	Creatinine	CREAT	Creatinine increased	High
Renal/kidney	Creatinine Clearance	CREATCLR	part of Chronic kidney disease	Low
Hematology				
Platelets	Platelets Count	PLAT	Platelet count decreased	Low
Red blood cells	Hemoglobin	HGB	Anemia/Hemoglobin increased	Low/High
White blood cells/differential	White Blood Cell Count	WBC	White blood cell decreased/Leukocytosis	Low/High
White blood cells/differential	Absolute Lymphocytes Count	LYM	Lymphocyte count decreased/increased	Low/High
White blood cells/differential	Absolute Neutrophils Count	NEUT	Neutrophil count decreased	Low

(1) According to CTCAE grade, if uric acid value is between ULN and 590 µmol/L it should be graded as following:

- Grade 1 if there are no physiologic consequences
- Grade 3 if there are physiologic consequences

For a programming perspective, values between ULN and 590 µmol/L will all be graded as Grade 1 (if any physiologic consequences are observed, it should be completed as an adverse event).

For all CTC gradable parameters, shift tables from baseline to worst grade on-treatment (including scheduled and unscheduled assessments) will be produced. The worst grade per subject will be defined as the highest CTC grade among the on-treatment evaluations. If there is

no on-treatment evaluation, then the worst grade will be set to 'Missing'. Parameters will be grouped by category.

Non-CTC gradable parameters

In this trial, non-CTC gradable parameters are displayed in table below

Category	Parameter (LBTEST)	Parameter code (LBTESTCD)	Direction of abnormality
Biochemistry			
Electrolytes	Phosphorus	PHOS	High/Low
Enzymes/cardial	Lactate dehydrogenase	LDH	High
Plasma proteins	Total protein	PROT	Low
Renal/kidney	Blood Urea Nitrogen	BUN	High
Hematology			
Red blood cells	Hematocrit	HCT	High/Low
Red blood cells	Mean Corpuscular Hemoglobin	MCH	High/Low
Red blood cells	Mean Corpuscular Hemoglobin Concentration	MCHC	High/Low
Red blood cells	Mean Corpuscular Volume	MCV	High/Low
Red blood cells	Red blood cells (Erythrocytes)	RBC	High/Low
Red blood cells	Reticulocytes	RETI	High/Low
White blood cells/differential	Basophils	BASOLE	High
White blood cells/differential	Eosinophils	EOSLE	High
White blood cells/differential	Monocytes	MONOLE	High/Low

Shift tables based on the normal range from baseline to worst on-trial value (including scheduled and unscheduled assessments) will be produced with the following categories for all hematology and blood chemistry parameters (CTC gradable and non-CTC gradable):

- Baseline: Low/Normal/High/Missing/Overall
- Worst On-trial: Low/Normal/High/Missing/Overall

Normal category includes low values for high parameters and high values for low parameters.

Only subjects with post baseline laboratory values will be included in these analyses.

All CTC gradable and non-CTC gradable parameters will be listed for each measurement (pre-treatment, on-treatment and post-treatment). Parameters will be grouped by category.

Listings will include at least the following items:

- Formulation
- Dose Level
- Subject identification number
- First / last dosing date

- Parameters
- Visit
- Date (Treatment day)
- Analysis value
- SI unit
- Change from baseline
- Reference range status (Low, Normal, High)
- CTC grade (with associated CTC name)
- Baseline flag (Yes/No)
- Worst value on-treatment flag (Yes/No)

In addition, a listing displaying parameters with at least one value with grade ≥ 3 will be provided. For each subject, only parameters where at least one value has Grade ≥ 3 will be displayed (all visits for the corresponding parameter will be displayed).

Coagulation parameters

All coagulation parameters will be listed for each measurement (pre-treatment, on-treatment and post-treatment).

Urinalysis

A listing of urinalysis and microscopic analysis will be provided.

15.5 Vital Signs

Population: SAF analysis set

Boxplots will be produced for systolic blood pressure, diastolic blood pressure, heart rate, temperature and weight. These will be presented by visit. Only scheduled visits will be taken into account.

Vital signs data from “Vital Signs” eCRF pages will be listed.

15.6 Other Safety or Tolerability Evaluations

15.6.1 Macroscopic signs of bleeding

Population: SAF analysis set

The macroscopic signs of bleeding will be listed at baseline and after administration of M3814 using data from “Macroscopic Signs of Bleeding” eCRF page.

15.6.2 ECOG Performance Status

Population: SAF analysis set

The listing will include all the data from the “ECOG Performance Status” eCRF section.

Additionally, one spaghetti plot per formulation/dose level will be produced, using different colors/line types per patient.

15.6.3 ECG and QT/QTc evaluations

Population: SAF analysis set

Electrocardiogram values based on “Triplicate 12-Lead ECG” eCRF section will be used for summary statistics and shift tables.

The number of subjects with normal ECGs at baseline and abnormal ECGs under treatment will be calculated.

If triplicate measurements are performed at any time point, the following will apply:

- The mean of the triplicate measurement will be used as summary of the quantitative parameters
- The worst Overall conclusion will be retained

Any unscheduled assessments that could be clearly identified as part of a triplicate measurement should be taken into account.

ECG parameters on-treatment will be presented by the following frequency table (by dose level and overall):

- Shift from normal baseline result to any abnormal post-baseline result
- Worst means absolute QTcF interval post-baseline
 - > 450 ms and ≤ 480 ms

- > 480 ms and \leq 500 ms
- > 500 ms
- Worst means QTcF increase from baseline
 - > 30 ms and \leq 60 ms
 - > 60 ms

Summary tables will be provided for each visit and time point by dose level and overall for the following ECG parameters

- Heart Rate
- R-R duration
- PQ/PR duration
- QT duration
- QR duration
- QTcF

ECG results (interpretation) will be summarized using a frequency table for each visit and time point by dose level and overall.

Visits and time points to be displayed in summary tables are:

- Baseline (corresponding to last measurement prior to the first dose of any trial treatment)
- Fraction day 1 post-dose (corresponding to ECG performed at 2 hours postdose for subjects enrolled under protocol V1.0 (collected in “ecg2” eCRF page) and at 2 to 3 hours postdose for subjects enrolled under protocol V1.0 or higher (collected in “ecg3” eCRF page))
- Fraction day 10

Two listings will display all the results as presented in “ECG” eCRF page, one on Qualitative Results and another one on Quantitative Results. All visits and time points will be included in listings.

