- r. Sparse PK samples will be collected as detailed in [Table 9](#). These sampling time points might be re-scheduled based on PK results from Phase Ia by the SMC.
- s. Mandatory archival tumor materials sampled before start of the treatment (most recent materials available). If no archival material is available then a fresh biopsy should be taken.

CCI

- v. PTD 210 and 312 will consist of phone calls to evaluate long term RT toxicity. No other assessments will be performed at these visits.
- w. Can be followed up via phone call every 3 months.

Table 5 Schedule of Assessments – Phase Ia (Arm B; SCCHN Cohort)

Trial Periods	Screening	DLT Evaluation Period					Mid-term Safety FU	Long-term Safety FU/ EOT ^a	Survival FU
		Treatment Period (M3814 + RT + Cisplatin)				DLT Period/ Short-term Safety FU			
Trial Days	Day -21 to Day -1	FD 1 to FD 33-35					PTD 1 to 35	PTD 1 to 90	PTD 31 to 365
M3814 RT 2 Gy x 33-35 (5 F/W) ^b Cisplatin	-	X X 100 mg/m ² twice (FD 1, 31) or 40 mg/m ² weekly					-	-	
Visit Days	-21 to -1	FD 1	FD 2	FD 6	FD 10 ^c	FD 16, 21, 26, 31 and last FD/ETT ^d	PTD 7, 14, 21, 28, 35 ^e	PTD 84	PTD 42, 126, 168, 180, 210 ^z , 270, 312 ^z , and 365
Visit Window (days)	-	-	-	-	-	-	±2	±7	±7
Signed informed consent	X								
Inclusion/exclusion criteria	X	X							
Demography	X								
Medical history	X								
Serum β-HCG pregnancy test (if applicable)	X					PTD 28 only			
Infection screen (hepatitis B and C), optional HIV test ^f	X								
HPV status in tumor ^g	X								
Audiogram ^h	X								
Vital signs ⁱ	X ^j	X		X	X	X	X	X	
Physical examination	X	X		X	X	X	X	X	X ^k
Clinical examination of bleeding	X	X		X	X	X	X		

Trial Periods	Screening	DLT Evaluation Period					Mid-term Safety FU	Long-term Safety FU/ EOT ^a	Survival FU
		Treatment Period (M3814 + RT + Cisplatin)				DLT Period/ Short-term Safety FU			
Trial Days	Day -21 to Day -1	FD 1 to FD 33-35					PTD 1 to 35	PTD 1 to 90	PTD 31 to 365
M3814 RT 2 Gy x 33-35 (5 F/W) ^b Cisplatin	-	X X 100 mg/m ² twice (FD 1, 31) or 40 mg/m ² weekly					-	-	-
Visit Days	-21 to -1	FD 1	FD 2	FD 6	FD 10 ^c	FD 16, 21, 26, 31 and last FD/ETT ^d	PTD 7, 14, 21, 28, 35 ^e	PTD 84	PTD 42, 126, 168, 180, 210 ^z , 270, 312 ^z , and 365
Visit Window (days)	-	-	-	-	-	-	±2	±7	±7
Esophageal endoscopy (if relevant)	X								
Evaluation of all tissues in RT area				X	X	X	X	X	X
ECOG PS	X				X	Last FD only	X	X	X
Adverse event assessment	X	X		X	X	X	X ^f	X ^f	
Concomitant medication	X	X		X	X	X	X		
Hematology ^m	X	X		X	X	X	X		

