- RT to be given 1.5 hours (± 30 minutes) after dosing.
- If FD10 is on a Friday, PK, PD, safety laboratory, and urinalysis sampling must be done on FD9.
- FD 33-35 is the day of the last dose of RT. In case of premature withdrawal during the treatment period, the investigations scheduled for the visit on the last FD should be performed. In such cases, this visit will be considered the Early Treatment Termination visit.
- All AEs will be collected from FD1 up to PTD 33-35 to evaluate the occurrence of DLTs.

- f. Hepatitis B and C testing to be performed at Screening unless obtained within 3 months prior to Screening. Screening for HIV will be performed according to local practice and local regulatory guidance.
- g. Immunohistochemistry in tumor material.
- h. As needed according to local guidelines.
- i. Heart rate, diastolic and systolic blood pressure, body temperature, and body weight. See Section [7.4.4](#) for details.
- j. Height measured at Screening only.
- k. Physical exam will report findings in the irradiated area during all FU periods.
- l. Evaluation of ongoing treatment-emergent adverse events.
- m. See [Table 15](#) for details of hematology tests.
- n. See [Table 15](#) for details of serum chemistry tests.
- o. Urinalysis: dipstick followed by microscopic examination if abnormal results.
- p. 12-lead resting ECG in triplicate.
- q. 12-lead ECG to be performed predose and once at 2 to 3 hours postdose.
- r. 12-lead ECG to be performed at 2 hours postdose.
- s. Tumor imaging by CT or MRI at baseline to document extent of lesions and absence of metastases (M0 stage) according to RECIST v1.1. Baseline tumor evaluation can be up to 28 days old when treatment starts.
- t. Tumor assessments to be done at long-term safety FU (every 6 weeks during Day 31-180 [4 assessments] and every 13 weeks during Day 181-365 [2 assessments]). Tumor assessment will not be repeated on PTD 180.
- u. PK samples will follow the sampling for Phase Ia as detailed in [Table 9](#). Sampling schedule may be changed by the SMC based on emerging data. See Section [7.5.1](#) for details.
- v. Predose only.
- w. Mandatory archival tumor materials sampled before start of the treatment (most recent materials available).

CCI

- z. PTD 210 and 312 will consist of phone calls to evaluate long term RT toxicity. No other assessments will be performed at these visits.
- aa. Can be followed up via phone call every 3 months.

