7.1.2 Treatment Period

7.1.2.1 Phase Ia Part: Arm A and Arm B (Fraction Days 1 to 10)

Eligible subjects will receive M3814 during the period in which RT is given.

The following assessments will be performed on Fraction Days 1, 6 and 10; if Fraction Day 10 is on a Friday, PK, CC1 safety laboratory, and urinalysis sampling must be done on Fraction Day 9:

- Review of inclusion and exclusion criteria (Fraction Day 1 only)
- Assessment of vital signs (blood pressure, heart rate, and body temperature), body weight (see Section 7.4.4 for details)

- Physical examination
- Clinical examination of bleeding (including petechiae, in skin, in the sclera of the eye, oral mucosa)
- Evaluation of all tissues in the RT area (Fraction Day 6 and 10 only)
- ECOG PS (Fraction Day 10 only)
- Assessment of AEs
- Documentation of concomitant medications
- Safety laboratory (hematology, serum chemistry and coagulation)
- Urinalysis (Fraction Day 10 only)
- 12-lead ECG including QTcF (Fraction Day 1 and 10)
- Collection of PK blood samples
- Availability of archival tumor material, either as a block or slides. If no archival material is available then a fresh biopsy should be taken

CCI

The following assessments will be performed on Fraction Day 2:

- Collection of PK blood samples (predose)

CCI

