8.5.4.3 Physical Examination

Physical examination, including vital signs (body temperature, heart rate, and blood pressure), and 12-lead ECG recorded at baseline and after administration of M3814 will be presented. Each ECG parameter will be summarized by descriptive statistics per time point, and changes from baseline will be calculated. A categorical analysis will be performed for QTcF data. Data will be further analyzed using concentration effect modeling for baseline-corrected QTcF values obtained at Day 1.

CCI

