8.2 Definition of Analysis Sets and Subgroups

All Subjects Analysis Set (ALL):

The All subjects (ALL) analysis set will include all the subjects who have signed the ICFs (i.e., screening failures plus subjects enrolled).

Safety Analysis Set (SAF):

The Safety analysis set will include all subjects who receive at least one administration of the trial treatment (either M3814, RT or Cisplatin).

Full Analysis Set (FAS):

The Full Analysis Set will include all subjects who receive at least one administration of the trial treatment.

Dose Escalation Analysis Set (DE) :

The Dose Escalation (DE) analysis set will include all subjects treated in dose escalation cohorts who receive at least 80% of M3814 and RT planned dose and complete the DLT period (through 5 weeks [Phase Ia, Arm A] or 12 weeks [Phase Ia, Arm B] after start of M3814 treatment). The DE set will also include subjects treated in dose escalation cohorts who experience a DLT during the DLT period regardless of the received amount of each drug.

Pharmacokinetics Analysis Set (PK):

The PK evaluation (PK) analysis set in Phase Ia and Phase Ib parts will include subjects who have received at least the first dose of the drug and provided PK samples as per protocol for at least 6 hours following first dosing on Fraction Day 1.

Table 1: Summary of analyses and associated analysis set

Analyses	ALL	SAF	FAS	DE	PK
Disposition and deaths	✓				
Baseline Assessments		✓			
Past and Concomitant Therapies		✓			
Compliance and Exposure		✓			

CONFIDENTIAL
INFORMATION

12/60

Analyses	ALL	SAF	FAS	DE	PK
Primary endpoint: DLTs				✓	
Secondary efficacy endpoints			✓		
Safety and tolerability		✓			
Biomarker		✓			
Pharmacokinetics					✓

9

General Specifications for Data Analyses

Statistical analyses will be performed with SAS 9.4 or higher.

Pooling of centers:

Because of the anticipated small number of subjects enrolled in each center, data will be pooled across centers, and the factor center will not be considered in statistical models or for subgroup analyses.

Presentation of continuous and qualitative variables:

All outputs will be provided for each arm separately. No data between arms will be pooled, unless otherwise stated. For each arm, data will be presented by formulation, dose level and overall unless specified otherwise. The dose level will be defined by the planned dose of the corresponding cohort. If several cohorts have same dose level, there will be pooled together for all summary outputs.

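### The SAP's by-visit ECG tables stop at fraction day 10 for both arms, leaving out 5 of the 7 scheduled on-treatment ECG days in Arm B (weeks 4 to 7)

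*SAP*

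**What the plan says.** SAP 15.6.3 makes two statements about by-visit ECG output. The first is general: "Summary tables will be provided for each visit and time point by dose level and overall for the following ECG parameters". Heart rate, RR, PQ/PR, QT, QR and QTcF follow, and ECG interpretation is to be tabulated in the same way. The second is a closed list, introduced by "Visits and time points to be displayed in summary tables are". Its entries are baseline, the FD1 post-dose recording and, last, "Fraction day 10". There is no Arm B version, although the SAP covers Phase Ia in both arms and section 9 states "All outputs will be provided for each arm separately".

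On the protocol side:

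- Section 8.5.4.3 sets the analysis commitment: "Each ECG parameter will be summarized by descriptive statistics per time point, and changes from baseline will be calculated".
- Section 7.1.2.1, which covers both arms up to FD10, schedules ECGs on FD1 and FD10.
- In Table 5 (Phase Ia, Arm B) the ECG row is also marked in the column headed "FD 16, 21, 26, 31 and last FD/ETT", and again at post-treatment day (PTD) 84 and in long-term follow-up. Section 7.1.2.2 repeats the ECG for the later fraction days.

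SAP section 7 lists departures from the protocol. It drops the concentration-effect model for QTcF, which comes from the same protocol section, but does not mention a restriction of ECG visits.

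**The concern.** The display list is exactly the on-treatment ECG schedule of the 10-fraction arm. Applied to the 33-to-35-fraction arm, it stops in week 2. ECG results are a secondary safety endpoint of Phase Ia in both arms. With the concentration-effect model dropped, the by-visit tables are the only planned central-tendency summary of QTcF, PR and QT.

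The remaining QTcF summaries are categories of the worst value, starting above 450 ms, and of the worst increase, starting above 30 ms. They cannot show a smaller average shift, and they do not show when a change arose. For subjects on the 100 mg/m² cisplatin schedule (FD1 and FD31), the by-visit tables end before the second cisplatin day.

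**Working it through.** The documents state no figure to reproduce. The check is a count, followed by a conversion of fraction days to calendar time.

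**Count of on-treatment ECG days, Phase Ia Arm B**

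- Scheduled (protocol Table 5, sections 7.1.2.1 and 7.1.2.2): FD1, 10, 16, 21, 26, 31 and last FD = 7.
- Displayed (SAP 15.6.3): FD1 and FD10 = 2.
- Omitted: 7 − 2 = 5, and 5/7 = 71%.
- Arm A: scheduled FD1 and FD10, both displayed, so none omitted.

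**Calendar position**

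At 5 fractions per week with no delay, fraction 5k + 1 falls on Day 7k + 1 for any weekday start:

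- FD16 (k = 3): Day 22, week 4
- FD21 (k = 4): Day 29, week 5
- FD26 (k = 5): Day 36, week 6
- FD31 (k = 6): Day 43, week 7

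The last fraction (FD33 to FD35) falls on Days 45 to 49, also week 7. All five omitted days therefore lie in weeks 4 to 7.

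**Length of treatment after the last displayed visit**

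| Start | FD10 | FD33 | FD35 | FD33 − FD10 | FD35 − FD10 |
|---|---|---|---|---|---|
| Mon | Day 12 | Day 45 | Day 47 | 33 | 35 |
| Tue | Day 14 | Day 45 | Day 49 | 31 | 35 |
| Wed | Day 14 | Day 45 | Day 49 | 31 | 35 |
| Thu | Day 14 | Day 47 | Day 49 | 33 | 35 |
| Fri | Day 14 | Day 47 | Day 49 | 33 | 35 |

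The gap is 31 to 35 calendar days. In fraction days, which are the days M3814 is given, it is 33 − 10 = 23 to 35 − 10 = 25.

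**Where the late ECGs do go**

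SAP section 9 defines on-treatment as Treatment Day 1 to 30 days after last dose, so FD16 to the last FD fall inside it. They enter the worst-QTcF and shift table in SAP 15.6.3, which is not tied to the visit list. The listings in the same section include all visits. ECGs at PTD 42, PTD 84 and later fall outside the 30 days and reach only the listings.

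**After the fix:** 7 of 7 Arm B on-treatment ECG days are displayed, and Arm A is unchanged.

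**The case against.** The best defence is that the list is a deliberate display choice. SAP version 2.0 added Arm B and, in the same revision, clarified which ECG visits to show. Protocol 7.4.4 gives ECG timing only for FD1 and FD10, and protocol 8.5.1 leaves analysis detail to the SAP. This may explain the list, but it does not cancel the later ECGs in Table 5 and section 7.1.2.2 or the per-time-point commitment in 8.5.4.3. A deliberate limit would still belong in SAP section 7 with a reason.

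A second defence is that by-visit means would say little. Cohorts are of 3, and about 30 Arm B escalation subjects are spread over dose levels and two formulations. This stands for the dose-level columns. The overall column is more informative, although it mixes doses.

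Three stronger readings are tempting and are not supported:

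- A reader might infer that the late Arm B ECGs are lost or that marked QTcF prolongation would go unseen. It would not: the worst-value categories, the shift to abnormal and the per-subject listings all use these recordings. ECG abnormalities that meet the criteria in protocol 7.4.1.1 are also reported as adverse events. Heart rate has by-visit boxplots under SAP 15.5. Outputs for the Safety Monitoring Committee are governed by a separate plan.
- A reader might extend the cisplatin point to all of Arm B. It applies only to the 100 mg/m² schedule; subjects on weekly 40 mg/m² are already receiving repeated doses by FD10.
- Subtracting the earliest FD10 from the latest FD35 gives 49 − 12 = 37 days, but the two cannot occur together. Day 12 needs a Monday start, and FD35 is then Day 47.

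**Conclusion.** The point holds as a gap in the by-visit ECG summaries of Phase Ia Arm B. Five of seven scheduled on-treatment ECG days are left out, all in weeks 4 to 7. No by-visit mean or change from baseline for QTcF, PR or QT is shown for the 31 to 35 calendar days (23 to 25 fraction days) after FD10. SAP 15.6.3 is inconsistent with itself for this arm and departs from protocol 8.5.4.3 without declaring it.

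The consequence is a missing description of average change and its timing, not a loss of data or of outlier detection. Arm A loses no on-treatment day. The calendar figures assume no radiotherapy delay (up to 7 days in total is allowed) and a completed course; an early-termination visit could fall sooner.

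Separately, footnote r of Table 5 ("12-lead ECG to be performed at 2 hours postdose") is attached to the PTD 84 and long-term ECGs, when M3814 is no longer given. Footnote q of Table 6 (Phase Ib, outside this SAP) does the same. This is a protocol inconsistency and does not bear on the count above.

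**What to change.** In SAP 15.6.3, extend the display list for Arm B with: Fraction Days 16, 21, 26, 31 and last Fraction Day/ETT (value and change from baseline). If the sponsor prefers the shorter list, SAP section 7 should declare the restriction and give the reason.

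The cost is a few extra rows in existing Arm B tables, from data already collected. Numbers per dose level will be small, so the overall column should carry most of the interpretation.

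As a separate protocol matter, the post-dose timing in Table 5 footnote r and Table 6 footnote q must be reconciled with the post-treatment visits to which they are attached.
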